Abbreviations and Special Terms	Definition
HIPAA	Health Insurance Portability and Accountability Act of 1996
HIV	human immunodeficiency virus
HRT	hormone replacement therapy
IB	Investigator's Brochure
ICF	informed consent form
ICH	International Council for Harmonisation of Technical Requirements for Pharmaceuticals for Human Use
ID	identification
IEC	Independent Ethics Committee
IFN	interferon
IGA	Investigator's Global Assessment
IGA-TS	Investigator's Global Assessment-Treatment Success (IGA score of 0 or 1 with \geq 2-grade improvement from baseline)
IL	interleukin
IRB	institutional review board
IRT	interactive response technology
ITCH4	\geq 4-point improvement in WI-NRS score
ITT	intent-to-treat
JAK	Janus kinase
[REDACTED]	[REDACTED]
MedDRA	Medical Dictionary for Regulatory Activities
NRS	numeric rating scale
OLE	open-label extension
[REDACTED]	[REDACTED]
RNA	ribonucleic acid
RSI	Reference Safety Information
SAE	serious adverse event
SAP	Statistical Analysis Plan
SoA	schedule of activities

Abbreviations and Special Terms	Definition
SOP	standard operating procedure
STAT	signal transducer and activator of transcription
STD	standard deviation
TEAE	treatment-emergent adverse event, AEs reported for the first time or worsening of a pre-existing event after first dose of study treatment
ULN	upper limit of normal
VC	vehicle-controlled
WBC	white blood cell
WOCBP	women of childbearing potential

1. PROTOCOL SUMMARY

Protocol Title:

A Phase 2, Randomized, Double-Blind, Vehicle-Controlled Study of the Efficacy and Safety of Ruxolitinib Cream in Participants with Cutaneous Lichen Planus

Protocol Number: INCB 18424-216

Objectives and Endpoints:

[Table 1](#) presents the primary and major/key secondary objectives and endpoints.

Table 1: Primary and Secondary Objectives and Endpoints

Objectives	Endpoints
Primary	
To establish the efficacy of ruxolitinib 1.5% cream BID in participants with cutaneous LP.	IGA-TS response (defined as an IGA score of 0 or 1 with \geq 2-grade improvement from baseline) at Week 16. [Proportion of participants achieving IGA-TS at Week 16]
Secondary	
To further assess the treatment effects of ruxolitinib 1.5% cream BID in participants with cutaneous LP.	
IGA-TS response at each scheduled postbaseline visit up to and including Week 32. [Proportion of participants achieving IGA-TS at each scheduled postbaseline visit]ITCH4 response (defined as a \geq 4-point improvement in Itch NRS score from baseline) at each scheduled postbaseline visit up to and including Week 32. [Proportion of participants with ITCH4 at each scheduled postbaseline visit]Time to achieve ITCH4.Change from baseline in the Skin Pain NRS score at each scheduled postbaseline visit up to and including Week 32.
To evaluate the safety and tolerability of ruxolitinib 1.5% cream BID.	
The type, frequency, and severity of AEs, including changes in vital signs and clinical laboratory blood samples.

Overall Design:

[Table 2](#) presents the key study design elements. Further study details are presented after the table.

Table 2: Key Study Design Elements

Study Phase	Phase 2
Clinical Indication	Treatment of patients with cutaneous LP
Population	Male and female participants at least 18 years of age who have predominantly cutaneous LP (covering \leq 20% BSA) and baseline IGA score \geq 3.
Number of Participants	Approximately 60 participants will be randomized 1:1 to 1 of 2 treatment groups (ruxolitinib 1.5% cream BID or vehicle cream BID).
Study Design	This is a 16-week, randomized, DBVC study with a 16-week OLE period with a crossover to active treatment for participants who complete the 16-week DBVC period (vehicle cream), followed by a 30-day post-treatment, safety follow-up visit. Participants initially randomized to the active treatment arm will continue with ruxolitinib 1.5% cream during the OLE period.
Estimated Duration of Study Participation	Estimated total duration of participants is up to approximately 40 weeks, including up to 4 weeks for screening, up to 32 weeks for treatment, and 30 days for safety follow-up.
Data Safety Monitoring Board/Data Monitoring Committee	No

Treatment Groups and Duration:

This is a Phase 2, randomized, DBVC study with a DBVC period of 16 weeks followed by an OLE period of 16 weeks. Participants who were initially assigned to ruxolitinib 1.5% cream will continue with active treatment during the OLE period, while those participants who were initially assigned to vehicle will cross over to active treatment.

Approximately 60 participants will be randomized 1:1 to either ruxolitinib 1.5% cream or vehicle cream (see [Figure 1](#)). Participants will be stratified by baseline IGA score (3 or 4). Participants will apply either ruxolitinib 1.5% cream or vehicle cream (both BID) through Week 16 to all affected areas identified at baseline. At Week 16, participants who meet the criteria (compliant with the Protocol and without safety concerns) will enter the 16-week OLE period. Participants randomized to vehicle in the VC period will be crossed over to ruxolitinib 1.5% cream, and participants randomized to ruxolitinib 1.5% cream at baseline will continue to apply ruxolitinib cream through Week 32. In the OLE period, participants will only treat active lesions. At Week 16, the LP treatment area will be evaluated by the investigator to assess the disease and confirm whether treatment continuation is required (IGA score \geq 1) during the OLE period or can otherwise (re)enter an observation/no treatment cycle (IGA score = 0). Treatment assignment during the DBVC period will remain blinded until all participants have completed treatment or discontinued.

[Table 3](#) presents the SoA. Adherence to the study design requirements, including those specified in the SoA, is essential and required for study conduct.

The COVID-19 global pandemic may present challenges to the normal conduct of this study (including AE and laboratory assessments), requiring the implementation of potential mitigation strategies described in [Appendix B](#).

Figure 1: Study Design Schema

[figure not shown]

Table 3: Schedule of Activities

Visit Day (Range)	Screening	Days -28 to -1	DBVC Period						OLE Period					Safety Follow-Up
		Baseline/ Day 1 (± 3 d)	Wk 2 ^a (± 3 d)	Wk 4 ^a (± 3 d)	Wk 8 ^a (± 3 d)	Wk 12 ^a (± 3 d)	Wk 16/ EOT1 ^b (± 3 d)	Wk 18 ^a (± 3 d)	Wk 20 ^a (± 3 d)	Wk 24 ^a (± 3 d)	Wk 28 ^a (± 3 d)	Wk 32 EOT2/ET ^c (± 3 d)	Unscheduled Visit	
Administrative procedures														
Informed consent		X												
Inclusion/exclusion criteria review	X	X												
Demography and medical history	X													
Prior/concomitant medications	X	X	X	X	X	X	X	X	X	X	X	X	X	
Contact IRT	X	X	X	X	X	X	X	X	X	X	X			
Distribute reminder cards	X	X	X	X	X	X	X	X	X	X	X			
Distribute eDiary	X													
Apply study drug in clinic		X	X	X	X	X	X	X	X	X	X			
Weigh/dispense study drug		X	X	X	X	X	X	X	X	X	X			
Collect/weigh study drug			X	X	X	X	X	X	X	X	X	X		
Assess study drug compliance			X	X	X	X	X	X	X	X	X			
Safety assessments														
AE assessments	X	X	X	X	X	X	X	X	X	X	X	X	X	
Comprehensive physical examination ^d	X											X		
Height and body weight	X											X		
Vital signs	X	X	X	X	X	X	X	X	X	X	X	X	X	
Physician-reported outcomes														
IGA	X	X	X	X	X	X	X	X	X	X	X	X		
%BSA ^e	X	X	X	X	X	X	X	X	X	X	X	X		
Target lesion assessment ^f		X												

Table 3: Schedule of Activities (Continued)

Visit Day (Range)	Screening	Days -28 to -1	DBVC Period						OLE Period					Safety Follow-Up
		Baseline/ Day 1 (\pm 3 d)	Wk 2 ^a (\pm 3 d)	Wk 4 ^a (\pm 3 d)	Wk 8 ^a (\pm 3 d)	Wk 12 ^a (\pm 3 d)	Wk 16/ EOT1 ^b (\pm 3 d)	Wk 18 ^a (\pm 3 d)	Wk 20 ^a (\pm 3 d)	Wk 24 ^a (\pm 3 d)	Wk 28 ^a (\pm 3 d)	Wk 32 EOT2/ET ^c (\pm 3 d)	Unscheduled Visit	
Patient-reported outcomes														
Itch NRS			Completed each evening through the last application of study drug.											
Skin Pain NRS														
Laboratory assessments														
Chemistry assessments	X	X ^h			X		X			X		X	X ⁱ	X
Hematology assessments	X	X ^h			X		X			X		X	X ⁱ	X
FSH ^j	X													
Serum pregnancy test ^k	X													
Urine pregnancy test ^k		X	X	X	X	X	X	X	X	X	X	X	X	X
Hepatitis/HIV serology	X													
Drug exposure assessments														

^a Visits at Weeks 2, 4, 8, 12, 18, 20, 24, and 28 can be performed virtually (through telemedicine if applicable) only due to COVID-19-related reasons. No efficacy assessments can be performed virtually (see [Appendix B](#)).

^b All Week 16 assessments must be completed before the participant can continue in the OLE period. Study drug will not be applied in the clinic at Week 16 for participants not continuing into the OLE period.

^c Participants who withdraw from the study early should complete the ET and the safety follow-up visits.

^d Targeted physical examinations can be performed for assessment of AEs and during other visits, including unscheduled visits, as per discretion of the investigator.

^e The total %BSA affected should be \leq 20% to be eligible for study entry and continued participation.

^f Target lesions typical of LP (3 or more) will be identified at baseline.

^h Not necessary if screening assessment is performed within 14 days of Day 1.

ⁱ Laboratory assessments are optional during unscheduled visits based on investigator's discretion and clinical judgment.

^j Women of nonchildbearing potential only. FSH is not needed in women with documented hysterectomy, bilateral salpingectomy, or bilateral oophorectomy.

^k Female participants of childbearing potential will have a serum test at screening, a urine pregnancy test before Day 1 study cream application, and a urine test at other visits noted. A positive urine test must be confirmed by a serum test.

[REDACTED]

[REDACTED]

[REDACTED]

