3. OBJECTIVES AND ENDPOINTS

[Table 4](#) presents the objectives and endpoints.

Table 4: Objectives and Endpoints

Objectives	Endpoints
Primary	
To establish the efficacy of ruxolitinib 1.5% cream BID in participants with cutaneous LP.	IGA-TS response (defined as an IGA score of 0 or 1 with \geq 2-grade improvement from baseline) at Week 16. [Proportion of participants achieving IGA-TS at Week 16]
Secondary	
To further assess the treatment effects of ruxolitinib 1.5% cream BID in participants with cutaneous LP.	
IGA-TS response at each scheduled postbaseline visit up to and including Week 32. [Proportion of participants achieving IGA-TS at each scheduled postbaseline visit]ITCH4 response (defined as a \geq 4-point improvement in Itch NRS score from baseline) at each scheduled postbaseline visit up to and including Week 32. [Proportion of participants with ITCH4 at each scheduled post-baseline visit]Time to achieve ITCH4.Change from baseline in the Skin Pain NRS score at each scheduled postbaseline visit up to and including Week 32.
To evaluate the safety and tolerability of ruxolitinib 1.5% cream BID.	The type, frequency, and severity of AEs, including changes in vital signs and clinical laboratory blood samples.

Table 4: Objectives and Endpoints (Continued)

Objectives	Endpoints

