6. STUDY TREATMENT

6.1. Study Treatments Administered

Ruxolitinib cream or matching vehicle will be applied as a thin film BID, with applications approximately 8 to 12 hours apart in the morning and in the evening at least 1 hour before bedtime.

At the baseline visit, an estimate of the %BSA to be treated will be used by the IRT system to calculate the number of tubes of study cream to be dispensed. During clinic visits, the participant should apply a thin film of study cream in front of site staff until all the affected areas to be treated are covered. This supervised application will be limited to 1 application of the study drug during the clinic visit. All areas identified at baseline should continue to be treated through the end of the DBVC period (Week 16) unless the participant meets criteria for stopping study cream. If there are new areas to be treated, including expansion of existing areas or development of new areas, after consultation with the investigator, study cream should be applied to these areas in addition to the areas treated at baseline (total affected areas \leq 20% BSA), and the percentage of BSA to be treated will be recalculated and increased. This new estimate will be entered into the IRT system to calculate the number of tubes of study cream to be dispensed. Participants whose new areas to be treated in addition to the areas identified at the baseline visit exceed 20% BSA should be discontinued from study treatment and the EOT assessment should be completed.

During the OLE period, starting at the Week 16 visit, the LP treatment areas will be evaluated by the investigator to assess if they still have disease and confirm whether the participant requires continuation of therapy (IGA score \geq 1) or can otherwise (re)enter the observation/no treatment cycle (IGA score = 0). Participants will stop treatment applications 3 days after all LP signs and symptoms have resolved. Multiple cycles of treatment/no treatment may be utilized as needed and treatment start/stop dates should be recorded by the participant in their eDiary. At any time during the OLE period, if a participant's new areas to be treated in addition to the areas identified at the previous visit exceed 20% BSA, then the participant should be discontinued from study treatment and the EOT assessment should be completed.

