8.2.8. Patient-Reported Outcomes

Patient-reported outcomes will be collected and assessed as outlined in the SoA (see [Table 3](#)). For all patient-reported outcome assessments conducted at the study site, in order to avoid bias in the participants' responses to the questionnaires, assessments should be completed before any other evaluations or study procedures on the day of the study visit and prior to treatment-related discussions with the investigator or study site staff.

8.2.8.1. eDiary Assessments

The participant will be instructed to complete and record their Itch NRS and Skin Pain NRS scores via eDiary every evening beginning on the day of screening through Week 32 or ET.

Both the Itch NRS and Skin Pain NRS are a daily participant-reported measure (24-hour recall) of the worst level of itch or skin pain intensity related to LP.

The participants will rate the following:

- Itch NRS: Itch severity of their LP by selecting a number from 0 (no itch) to 10 (worst imaginable itch) that best describes their worst level of itching in the past 24 hours.
- Skin Pain NRS: Pain severity of their LP by selecting a number from 0 (no pain) to 10 (worst imaginable pain) that best describes their worst level of pain in the past 24 hours.

The average of the 7-day Itch NRS score prior to the baseline visit (minimum 4 out of 7 days' data required) will be used to determine if a participant meets the inclusion criteria.

Detailed directions for the administration of the eDiary will be provided in the Study Manual.

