8.8. Follow-Up

8.8.1. Safety Follow-Up

The safety follow-up period is the interval between the Week 32 (EOT2)/ET visit and the scheduled follow-up visit, which should occur 30 days (+ 7 days' visit window) after the Week 32 (EOT2)/ET visit (or 30 days after the last application of study drug if the Week 32 (EOT2)/ET visit was not performed). Participants who have been in an observation/no treatment cycle from Week 28 or earlier until Week 32 do not need to complete the safety follow-up visit.

Adverse events and SAEs must be reported up until 1) at least 30 days after the last application of study drug or 2) until toxicities resolve, return to baseline, or are deemed irreversible, whichever is longer. Reasonable efforts should be made to have the participant return for the follow-up visit and report any AEs that may occur during this period.

9. ADVERSE EVENTS: DEFINITIONS AND PROCEDURES FOR RECORDING, EVALUATING, FOLLOW-UP, AND REPORTING

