7.4.3. Time-To-Event Efficacy Endpoint

The time to achieve Itch NRS score improvement of at least 4 points from baseline (ie, ITCH4) will use the daily Itch NRS score in comparison to baseline Itch NRS score in the DBVC period. A log-rank test stratified by randomization stratification factor, baseline IGA score (3 or 4), will be used for between-treatment group comparisons. The hazard ratio and its 95% CI will be estimated based on the stratified Cox regression model using Efron's method accounting for ties. Kaplan-Meier curves will be presented by treatment groups. The number of participants, number of participants with events, and number of participants censored will be summarized by treatment group. The Kaplan-Meier estimate of median time will be presented with its 95% CI. The 95% CI will be calculated using the method by Brookmeyer and Crowley (1982).

The last available value for time to ITCH4 during the DBVC period is the last nonmissing measurement obtained after the first application of study cream and within 30 days after the last application of study cream in DBVC period, or before the first application of study cream in the OLE period, whichever is earlier.

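### The documents give three different ends for nightly itch and skin pain entry; following the Schedule of Activities would drop open-label scores from participants who clear

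*Protocol*

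**What the plan says.** **End of entry.** Three wordings govern the same diary.

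- Protocol Table 3, patient-reported outcomes: "Completed each evening through the last application of study drug".
- Protocol 8.2.8.1, for both scales: "via eDiary every evening beginning on the day of screening through Week 32 or ET".
- SAP 7.2.6.1 (itch) and 7.2.6.2 (skin pain): from screening to Week 32 or treatment discontinuation.

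**What the scores are for.** Protocol Table 4 lists as a secondary endpoint "Change from baseline in the Skin Pain NRS score at each scheduled postbaseline visit up to and including Week 32". ITCH4 response has the same horizon.

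**Why cream can stop before Week 32.** For the OLE, Protocol 6.1 says "Participants will stop treatment applications 3 days after all LP signs and symptoms have resolved" and "Multiple cycles of treatment/no treatment may be utilized as needed". Participants with IGA 0 at Week 16 may go straight into observation. Protocol 6.5 counts OLE clearance as a temporary interruption. Protocol 8.8.1 has a rule for participants "in an observation/no treatment cycle from Week 28 or earlier until Week 32".

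**Start of entry.** Protocol 8.2.8.1 and the SAP start on the day of screening. Protocol 8.1.4 issues the device at screening but says use of its eDiary starts on Day 1. Inclusion criterion 6 needs at least 4 of the 7 daily itch scores before Day 1.

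**The concern.** Last application and Week 32 are the same date only for someone who uses cream to the end. For a participant who clears in the OLE and does not restart, Table 3 ends the diary weeks before Protocol 8.2.8.1 does. Because cycles can repeat, nobody at the site can know at the time which application will be the last.

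Protocol Section 1 makes adherence to the Schedule of Activities mandatory, and Protocol 8.2.8 refers to that schedule for collecting these outcomes, so a site has reason to follow Table 3. If it does, scores disappear because the participant cleared. SAP 7.2.6.1 states nonresponder imputation for the double-blind (DBVC) period only, and SAP 7.2.6.2 allows no imputation for skin pain. A 24-hour recall score that was never entered cannot be recovered later.

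**Working it through.** **Inputs**

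- Visit score: the mean of the seven daily scores before the visit day, missing if four or more are absent (Protocol 10.4.2; SAP 7.2.6.1 and 7.2.6.2).
- Last OLE application: 3 days after clearance (Protocol 6.1).
- OLE visits: Weeks 18, 20, 24, 28 and 32, each ±3 days (Protocol Table 3). These fall 14, 28, 56, 84 and 112 days after Week 16.

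The plan gives no figure of its own on this point. Its one computed design figure, power above 80%, reproduces (Fisher exact test, 30 per arm, 58% against 20%: 0.810) and does not depend on the diary.

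**Step 1: when a visit is lost.** If the last entry is k days before the visit (k from 1 to 8), the scores available are 8 − k.

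- k = 4: 4 present, 3 missing, so the visit score is kept.
- k = 5: 3 present, 4 missing, so the visit score is lost.

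**Step 2: in terms of clearance.** With clearance d days before the visit, the last entry is d − 3 days before it. The score is lost when d − 3 ≥ 5, that is, d ≥ 8.

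**Step 3: visits lost per participant if Table 3 is followed and cream is not restarted**

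| Clear at | Last entry, days after Week 16 | Gap to next visit (days) | Visits lost |
|---|---|---|---|
| Week 16 (IGA 0, no OLE cream) | 0 at the latest | 14 or more | 18, 20, 24, 28, 32 (five) |
| Week 18 | 14 + 3 = 17 | 28 − 17 = 11 | 20, 24, 28, 32 (four) |
| Week 20 | 28 + 3 = 31 | 56 − 31 = 25 | 24, 28, 32 (three) |
| Week 24 | 56 + 3 = 59 | 84 − 59 = 25 | 28, 32 (two) |
| Week 28 | 84 + 3 = 87 | 112 − 87 = 25 | 32 (one) |

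Visit windows do not change this. The smallest gap is 11 days; one visit 3 days late and the next 3 days early leave 11 − 6 = 5, still lost. After a restart, only visits with four or more entry-free days in their window are lost.

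The Week 16 row matters for the ITT by-visit summaries (SAP 7.4 and Appendix A). A participant who applies no cream in the OLE is not in the OLE evaluable population (SAP 5.3.3).

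**Step 4: direction.** Let c be the share of a group lost this way, pc the ITCH4 proportion among them and pn the proportion among the rest. The full-data proportion is c·pc + (1 − c)·pn and the observed-case proportion is pn, so the error is −c(pc − pn). It is negative whenever cleared participants respond more often.

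An illustration only, on values that are in neither document: with c of 5% to 25%, pc of 90% to 100% and pn of 40% to 60%, the shortfall runs from 0.05 × (0.90 − 0.60) = 1.5 points to 0.25 × (1.00 − 0.40) = 15 points.

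**Step 5: start of entry.** Baseline uses Days −7 to −1. Entry from Day 1 supplies 0 of these 7 scores, against the minimum of 4 in criterion 6. Taken literally, that leaves no baseline for either scale.

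**The case against.** The best defence is that Table 3 is shorthand for the end of treatment. Protocol 8.7 places that at Week 32, Protocol 6.5 treats clearance as an interruption, and Protocol 6.1 has participants log treatment start and stop dates in the same eDiary, so the device stays in use. A site that cannot identify the last application also has no clear trigger to stop the diary. The Study Manual, which is not available here, may settle the matter. This makes continued entry the likelier intention, and many sites may do it. It does not remove the conflict: Protocol 8.8.1 foresees participants whose last application was at or before Week 28, and no text says that Table 3 yields to 8.2.8.1.

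The stakes are also limited. No test is planned after Week 16 on these outcomes in the public text, and everyone on treatment by then uses active cream. That stands, and it limits the weight of the point.

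In the extracted table the stop wording sits on the itch row and the skin pain row is blank. I read it as one cell covering both, because 8.2.8.1 gives the scales one rule. If that is wrong, the Table 3 conflict concerns itch alone.

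A reader might infer from SAP 7.4.3, which admits itch values "within 30 days after the last application of study cream in DBVC period", that the SAP expects the diary to outlast treatment. That does not follow. The sentence is an analysis cut-off for time to ITCH4, it also closes at the first OLE application, and SAP 7.2.6.1 ends entry at treatment discontinuation.

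On 8.1.4, the neighbouring sentences concern recording of applications, so Day 1 may refer only to that log. Criterion 6 would expose a literal reading with the first participants screened. The text does not make the distinction, so it still needs correcting.

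**Conclusion.** The three end points conflict as written and should be reconciled. If Table 3 is followed, a participant who clears and does not restart loses one to five OLE visit scores on each scale. The descriptive Week 18 to 32 ITCH4 and Skin Pain summaries would then probably understate improvement. The direction assumes that OLE values are analysed as observed and that cleared participants improve more than others. It is less sure for skin pain, which has no minimum baseline score at entry.

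The size is unknown. It depends on how many sites follow Table 3 and how many participants clear and stay off cream. A reader might borrow the cited open-label study, where 2 of 12 were fully clear at Week 4. That was a Patient Global Assessment, not IGA 0 or resolution of all signs and symptoms, and it does not support a count here. The percentage points in the illustration are not estimates.

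A reader might also infer that the main results are at risk. The documents do not support this for the stop conflict. Cream is applied continuously to Week 16, so the Week 16 ITCH4 test and DBVC time to ITCH4 are not materially affected, and the primary endpoint does not use the diary.

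The Day 1 start in 8.1.4 is a separate defect. Its literal consequence is larger, because it removes every baseline, but it is likely to be noticed early.

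**What to change.** - **Protocol Table 3:** replace the last-application end point for the NRS assessments with *nightly to Week 32 or ET, observation/no-treatment cycles included*.
- **SAP 7.2.6.1 and 7.2.6.2:** use the same end point, and state that a no-treatment cycle is not treatment discontinuation.
- **Protocol 8.1.4:** state that NRS entry begins on the day of screening and that only application logging begins on Day 1.

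The cost is wording changes in the Protocol and SAP and a note to sites and the eDiary vendor. There are no new assessments: cleared participants keep the nightly entries that Protocol 8.2.8.1 already asks for.
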